### 1.2.3 HPV-associated OPSCC: A sensitive patient sub-population

OPSCC is increasing in incidence in the United States in non-traditional populations, i.e. non-ethanol and non-tobacco user groups, secondary to HPV-associated malignancies(12). Data from multiple studies reveal that oropharyngeal HPV-associated tumors account for 20-75% of oropharyngeal tumors(13, 14). HPV16 is the most common viral subtype associated with malignant transformation, as it is found in 90-95% of HPV-associated OPSCC(13). Over 86% of HPV-associated tumors over-express p16INK4A (p16), a cyclin-dependent kinase inhibitor, and only 3% of HPV-non-associated tumors over-express p16(15). P16 status can be identified easily by standard immunohistochemical techniques. Based on our own tissue microarray p16 immunohistochemical analysis, approximately 60% of oropharyngeal SCCs in central Virginia are HPV-associated(16).

Malignant transformation of HPV-associated malignancies involves the E6 and E7 oncoprotein pathways which functionally inactivate two human tumor-suppressor proteins, p53 and pRb respectively, leading to cellular proliferation, loss of cell cycle regulation, impaired cellular differentiation, increased frequency of spontaneous and mutagen-induced mutations, impaired apoptosis, and chromosomal instability(15, 17-19). The E6 oncoprotein binds to the cellular ubiquitin-protein ligase E6-AP and uses E6-AP to target the tumor suppressor protein p53 for ubiquitination and subsequent proteasome-mediated degradation. As a result of this degradation, p53 cannot initiate the apoptosis cascade or activate p21 to arrest the cell cycle. The overall effect is the abrogation of both the p53 and p21 pathways leading to impaired apoptosis and uncontrolled cellular growth(15, 17-19). The E7 oncoprotein can associate with both pRb and p21. In normal, non-proliferating cells, pRb blocks cell cycle progression by complexing with transcription factors such as E2F(18). When pRb is phosphorylated by cyclin-dependent kinase (CDK) complexes, it disassociates with E2F, enabling the cell to advance through the cell-cycle and divide. The p16 protein is a tumor suppressor that inactivates CDK4- and CDK6-cyclin D complexes and therefore suppresses the phosphorylation of pRb and protects against unregulated cell proliferation(15, 17). The binding of pRb by E7 prevents the pRb/E2F complex formation and leads to uncontrolled cell division(18). pRb acts as an inhibitor of p16 transcription, so pRb inactivation by E7 results in highly increased p16 expression in HPV-positive SCC(15). P16 is frequently inactivated epigenetically in HPV-non-associated tumors by means of hypermethylation(20).

HPV-associated tumors in the head and neck have been reported to be more sensitive to chemotherapy and radiation than non-HPV-associated tumors, and p16 status is a highly significant independent prognostic indicator for disease-free survival (DFS) with reported 5-year DFS of 84% for p16 positive (p16+)

tumors and 46% for p16 negative (p16-) tumors in one study(15). The use of p16 expression to predict DFS was superior to all clinicopathologic parameters normally used for treatment decisions and assessment of prognosis(15).

Additional studies have confirmed that p16 immunohistochemistry is the best test to use for risk stratification in oropharyngeal SCC regardless of HPV status(21). An Affymetrix Human U133A GeneChip analysis of HPV-positive SCC and HPV-negative SCC reported that these tumors also had different specific gene expression profiles(22). It is unknown why p16+ tumors are more radiation responsive, but it may be due to higher proliferation rates of these poorly differentiated tumors compared to p16- tumors since radiation preferentially kills mitotically active cells. Cells are most sensitive to radiation-induced damage in the G2 and M phases of the cell cycle(23).

### **1.3 Study Agent(s) Background and Rationale**

#### **1.3.1 Radiation-induced Xerostomia**

Xerostomia (dryness of the mouth) is the most prominent and common complication of radiotherapy for head and neck cancers (HNC), occurring in 60-90% of patients treated(24). During radiotherapy, the salivary glands may absorb enough radiation to impair or destroy their secretory function, thereby decreasing saliva production and causing xerostomia. The major salivary glands (parotid, submandibular, and sublingual) produce about 90% of salivary secretions while the remainder is produced by the minor salivary glands(24, 25). The parotid gland is extremely sensitive to radiation, and a median parotid dose of greater than 26 Gy results in permanent glandular atrophy and fibrosis(26). If both parotid glands are treated above tolerance, permanent xerostomia is likely to result. The resultant xerostomia in these patients contributes to a decrease in quality of life with adverse effects on speech, mastication, taste, swallowing, nutritional intake, and sense of well-being(24). Dryness of the oral mucosa also creates a predisposition to mucosal fissures and ulcers, and changes in the composition of the oral flora lead to dental caries and infections. The reduction in the salivary flow may also indirectly contribute to the risk of osteonecrosis of the mandible as abscessed mandibular teeth can lead to mandibular sequestration(24, 27, 28).

To relieve these symptoms, saliva substitutes are only temporarily effective and the usefulness of sialogogues, such as pilocarpine, is limited by cholinergic side effects(24). The administration of the radiation protector WR-2721 (amifostine) provides a benefit to a small proportion of head and neck cancer patients but often produces side effects including nausea and hypotension(29). On the other hand, the use of intensity modulated radiotherapy (IMRT) can sharply decrease the dose of radiation absorbed by one or part of both

parotid glands and thereby reduces xerostomia and improves quality of life(26, 30). Due to the sensitivity of the parotid glands (tolerance dose of 26 Gy median dose) and the need to treat adjacent nodal volumes to 50-70 Gy, the parotid glands are still near tolerance even with the most advanced treatment planning and delivery systems such as the Helical Tomotherapy system(31, 32). However, if the radiation dose to the electively treated cervical nodes could safely be reduced in patients with radiosensitive tumors, the dose delivered to the parotids would also be reduced and would therefore diminish the risk of xerostomia.

### **1.3.2 Intensity Modulated Radiation Therapy (IMRT)**

Radiation therapy techniques for oropharyngeal SCC have undergone rapid technical advancements with the development of intensity modulated radiation therapy (IMRT) and image guidance of daily treatments. IMRT is the use of radiation beam shaping through the optimization of multi-leaf collimator positions by opening and closing leaves to change the intensity of different portions of the beam. This shaping enables the radiation dose to conform more precisely to the three-dimensional shape of the tumor. In typical LINAC-based IMRT, combinations of several (usually 7 to 9) non-opposing intensity-modulated radiation fields are used to deliver highly conformal dose distributions to target volumes while sparing adjacent non-target tissues. Thus, IMRT treatment planning requires the contouring of normal organs at risk (OARs) and target volumes on a kilovoltage CT (kVCT) image set, followed by daily treatment usually delivered with CT image guidance.

The use of IMRT for HNC has achieved near-universal acceptance, with 100% of responding US radiation oncologists reporting its use in a 2009 survey(16). When used in the treatment of head and neck cancer, IMRT has been shown to cause less biologic injury to normal adjacent structures while maintaining similar or improved locoregional tumor control rates(30, 33-35). Multiple single-institution retrospective publications have described the outcomes of OPSCC patients treated with IMRT. For example, the use of IMRT in recent studies has yielded 2 and 3-year locoregional progression-free survival rates above 90%(1, 31, 36, 37), compared to rates of about 80% with non-IMRT techniques(36). Studies with IMRT have reported comparable acute toxicities to those of conventional therapy and even reduced late toxicities, as IMRT enables significant sparing of the parotid glands, resulting in reduced xerostomia and improved quality of life(26, 30, 33, 34, 38). Recent prospective randomized controlled trials (RCT) have confirmed that the use of IMRT results in less xerostomia than conventional RT for nasopharyngeal, oropharyngeal, and hypopharyngeal carcinomas(39-41). Of these RCTs, only Nutting et al mention

survival data, and they found no differences in overall survival or locoregional control rates between IMRT and conventional RT(40).

### **1.3.3 Helical Tomotherapy-based IG-IMRT**

The Helical Tomotherapy Technology (AccuRay, Sunnyvale, CA) is an image-guided IMRT unit based on helical CT technology and is a fully integrated treatment planning and image guided delivery system. The system has a 6 megavoltage (MV) linear accelerator, a 6.25 mm binary pneumatic multi-leaf collimator (MLC) for beam modulation, and a radiation detector allowing for fan beam megavoltage CT (MVCT) scan acquisition built onto a standard CT gantry. The inverse treatment planning system calculates the MLC position every 7 degrees of rotation or 51 times per gantry rotation. We have previously published results that show that the Helical Tomotherapy system provides improved dose homogeneity and normal structure dose compared with LINAC-based IMRT in the treatment of oropharyngeal carcinomas(32). This results in a reduced risk for complications from focal hotspots within the planning target volume and a reduced dose to the adjacent parotid glands(32). Daily MVCT images can be obtained and electronically co-registered to the planning kVCT scan, allowing for daily image guidance for highly accurate patient positioning prior to treatment. We have previously published that without image guidance, the patient isocenter vector can shift over 3mm between treatments and result in significant errors in dose delivery(42). We will deliver highly conformal IMRT to the patients in this study using image guided Helical TomoTherapy.

### **1.3.4 Dose Reduction to the N0 Neck Lymph Nodes in p16+ Patients**

Our research group performed a retrospective analysis of 112 patients at UVA with OPSCC who received IMRT, of which 72 had p16 immunohistochemical analysis of their corresponding biopsies(2). To the best of our knowledge, this study was the largest reported series of OPSCC patients definitively treated with IMRT at the date of publication and the only IMRT study reporting stratification for p16 tumor status for outcome analysis. The primary, pathologic nodal, and N0 nodal control rates at UVA for p16+, p16-, and p16 unknown patients are shown in Table 1 and Table 2 (Appendix A). This data confirms the findings of other investigators that patients with p16+ tumors have significantly better outcomes than patients with p16- tumors(15). In our study with a median follow-up of 29 months, we found that patients with P16+ tumors treated with chemoradiation (n=28) had 100% primary tumor local control, 90% sterilization of pathologic nodes based on neck dissection data, and 100% control of the N0 volumes(2).

Historically, Fletcher reported that 45-50 Gy was the necessary dose to treat the clinical N0 neck to achieve 90% chance of no nodal recurrence(43). The

N0 status was determined by physical examination only (in the pre-CT era) and was reported for radiation alone without chemotherapy. Harrison performed a meta-analysis to determine the dose response for local control of the N0 neck with radiation alone and reported that 45-50 Gy would result in a 95% chance of nodal control(44). Our data revealed 2/112 (1.8%) of patients with recurrence in the N0 cervical volumes; both had documented local recurrence of the primary, and neither was p16+. Isolated N0 nodal failure is defined as failure in an N0 volume without associated failure in the primary tumor, failure in known pathologic lymph node volume, or distant metastatic disease. Isolated N0 nodal failure in a CT or PET CT staged N0 nodal volume following 50 Gy with or without chemotherapy is rare and reported to occur in only about 2-3% of head and neck cancer patients(44-46). Our retrospective analysis found 0/112 (0%) of patients had isolated N0 lymph node failures, and p16+ patients who received chemoradiotherapy (n=28) had a 100% 3-year locoregional control rate. With such dramatic responses in p16+ patients, it is very likely that the N0 neck in this cohort is receiving more radiation than necessary. For comparison, cervical and anal cancers are also squamous cell carcinomas associated with HPV, but their N0 nodes are treated with lower radiation doses than those in head and neck cancer. In contrast to the 50 Gy delivered to the N0 neck in HNC, N0 inguinal nodes in anal cancer are often only treated to 30.6 Gy(47, 48), and N0 para-aortic nodes in cervical cancer receive 44 Gy(49). Thus, a reduction of the dose to the N0 neck in p16+ OPSCC to 39.6 Gy is consistent with doses already utilized with similar cancer histology in other anatomic sites.

### **1.3.5 Post-treatment Surveillance with PET-CT**

Patients with head and neck cancer are often monitored after treatment with PET CT, as it has been shown to be highly sensitive in the detection of persistent and recurrent disease after treatment(50-52). Multiple studies show that an initial negative PET CT obtained 3 months after definitive radiotherapy can have a negative predictive value (NPV) as high as 100% for locoregional recurrence with an average NPV of 95%(50-52). However, sensitivity of PET is slightly lower for distant metastases(51, 52). Most authors recommend follow-up PET CT from 3 to 6 months after completion of treatment because studies have shown higher false-negative PET scans when obtained less than 3 months after treatment(50, 51, 53, 54). Thus, a negative PET scan 3 to 6 months after treatment may have a very high probability of ruling out any locoregional recurrence in patients who receive a lower dose to the N0 neck.

If a locoregional recurrence is going to occur, it is most likely to recur within 1 to 2 years, as nearly 90% of all HNC failures occur within the first 2 years after treatment(36). Yao et al (2005) found that 11/150 (7.3%) HNC

patients treated with IMRT developed locoregional recurrences in a median time of about 5 months (range of 2 to 16 months)(37). Their local recurrence-free survivals at 2 and 3 years were equivalent at 94%, and locoregional recurrence-free survivals at 2 and 3 years were also equivalent at 92%. Eisbruch et al reported a 16% rate of locoregional recurrence at a median time of 8 months (55), while Huang et al (2008) reported 10% developing locoregional recurrences at a median time of 15 months (range of 3 to 43 months)(31). Thus, any patient disease-free at 2 years has a very high likelihood of remaining disease-free. However, data is not available for the recurrence of the N0 volumes in the above studies, and they did not stratify their data according to p16 status, which provides vital prognostic significance. Our p16+ patients had 100% control of the N0 volumes at 3 years after treatment, so any isolated recurrence in the N0 volumes after dose reduction at any time in this current study would be suspicious for an inferior treatment.

However, post-treatment PET CT imaging is not the national standard of care following definitive treatment of squamous cell carcinomas of the head and neck. Post-treatment PET CT imaging will therefore be optional on this study and can be used if post treatment contrast enhanced CT or MRI scans show equivocal results and/or the patient declines a recommended neck dissection.

#### **1.4 Rationale for Study Design**

This is an unblinded, single arm study to demonstrate that reduced intensity radiation of the N0 nodes in patients (n=45) with p16+ oropharyngeal squamous cell carcinoma can provide improved tolerability compared with historic controls. The results of this study will support future studies to establish the equivalent efficacy and improved toxicity profile of this treatment in a larger population.

## **2 STUDY OBJECTIVES**

### **2.1 Primary Objectives**

- 2.1.1** To estimate the N0 nodal control rate in patients with p16+ oropharyngeal squamous cell carcinoma (OPSCCA) treated with 39.6 Gy to the clinically uninvolved cervical lymphatics.

### **2.2 Secondary Objectives**

- 2.2.1** To evaluate safety and tolerability of treatment of p16+ OPSCCA treated with 39.6 Gy to the clinically uninvolved neck by overall incidence of adverse events, incidence of acute and late radiation-induced toxicities and subject-rated quality of life assessments.

**2.2.2** To estimate progression-free survival and locoregional recurrence-free survival in patients with OPSCCA following treatment with 39.6 Gy to the clinically uninvolved neck.

**2.2.3** To compare the dose volume histograms (DVH) of treatment plans for patients receiving 39.6 Gy to the N0 neck to the DVH of matched treatment plans with the standard 50 Gy to the N0 neck.

### **3 PATIENT ELIGIBILITY**

#### **3.1 Inclusion Criteria**

**3.1.1** Patient must sign a study specific informed consent prior to study entry.

**3.1.2** Zubrod performance status 0-2.

**3.1.3** Age  $\geq$  18 years.

**3.1.4** Patients must be clinically referred for radiation therapy with stage I-IVb (T1-T4, N0-N3, M0) squamous cell carcinoma of the oropharynx.

**3.1.4.1** Tumor must be measurable by physical exam and or endoscopy, and PET CT. PET CT must be performed within 8 weeks of initiating treatment for cancer.

**3.1.4.2** Disease must be staged using the 2010 American Joint Cancer Committee Staging System (version 7).

**3.1.5** HPV (p16)-positive tumor confirmed by immunohistochemistry.

**3.1.6** Patient must be able to comprehend English (or a medical interpreter for their native language must be available for all study visits)

**3.1.7** Patient must be capable and reliable to participate in all study related procedures.

**3.1.8** Patient must be able to lie flat on the table for IMRT and tolerate aquaplast or other immobilization/image tracking systems that reduces intra-fraction motion to 3 mm or less.

#### **3.2 Exclusion Criteria**

**3.2.1** Patients may not be receiving any investigational agents.

**3.2.2** Prior radiotherapy to the head and neck in the volumes to be irradiated for this malignancy.

**3.2.3** Any other malignancy except non-melanomatous skin cancer or a carcinoma not of head and neck origin with the patient being disease free for  $\geq$  5 years.

**3.2.4** Nutritional and general medical condition are incompatible with the proposed radiotherapy treatment

**3.2.5** Any major medical psychiatric or neurologic illness, which in the investigators' opinions would interfere with either completion of therapy or with full and complete understanding of the risks and potential complications of the therapy.

**3.2.6** A serious uncontrolled medical disorder that is in the opinion of the Investigator would impair the ability of the patient to receive protocol therapy.

**3.2.7** Pregnant and breastfeeding women are excluded from this study.

**3.2.7.1** Women of childbearing potential must have a negative pregnancy test within 14 days prior to initiation of treatment.

**3.2.7.2** Women of childbearing potential and men must agree to use adequate contraception (hormonal or barrier method of birth control) prior to study entry and for the duration of study participation. Should a woman become pregnant or suspect she is pregnant while participating in this study, she should inform her treating physician immediately.

## **4 TREATMENT PLAN**

### **4.1 Registration**

Patients who meet eligibility criteria must be registered in OnCore. The following minimum registration information must be entered for all patients registered:

- demographics
- date of signed informed consent
- subject number
- on-study date (date subject meets all eligibility criteria)
- disease site
- registering investigator

### **4.2 Intensity Modulated Radiation Therapy (IMRT) Treatment Regimen**

Patients will be treated on a Helical Tomotherapy Unit (AccuRay, Sunnyvale, CA) over a period of 7 weeks. Patients will receive IMRT to two regions:

Planning Target Volume 1 (PTV1), which includes the gross disease (GTV) with expansions for microscopic disease extension and 3 mm setup error expansion; and Planning Target Volume 2 (PTV2), which includes the clinically uninvolved cervical lymph nodes (N0 lymph node volumes) with a 3 mm expansion for setup error. PTV1 will receive 70 Gy/35 fractions at 2.0 Gy/fraction/day for 5 days/week. PTV2 will be treated to 39.6 Gy/22 fractions at 1.8 Gy/fraction/day for 5 days/week.

#### **4.3 Dosing Delays/Dose Modifications**

Any patient who receives treatment on this protocol will be evaluable for toxicity. Each patient will be assessed periodically for the development of any toxicity according to the Time and Events table (See Section 5). Toxicity will be assessed according to the NCI Common Toxicity Criteria for Adverse Events (CTCAE), version 4.0 (See Appendix A).

Treatment breaks, if necessary, ideally should not exceed 5 treatment days at a time and 10 treatment days total. Treatment breaks should be allowed only for resolution of severe acute toxicity and/or for intercurrent illness and not for social or logistical reasons. Treatment breaks must be clearly indicated in the treatment record along with the reason(s) for the treatment break(s). Any treatment break(s) exceeding 2 treatment days for reasons other than toxicity/illness will be considered a protocol deviation.

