#### 4.7 Duration of Follow Up

Patients will be followed for three years after completion of the treatment or withdrawal from the study, or until death (whichever occurs first). All patients, regardless of the duration of therapy, will be asked to complete QOL questionnaires every 3 months for the first year (starting at 6 months post-IMRT), and every 6 months for the second and third years.

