**Table 2: Follow-Up Assessments**

	Months  following last IMRT									
	3	6	9	12	15	18	21	24	30	36
Contrast enhanced CT (or MR) or PET CT	X 			X				X		X
QOL questionnaires 	X	X	X	X	X	X	X	X	X	X
History	X	X	X	X	X	X	X	X	X	X
Physical Exam 	X	X	X	X	X	X	X	X	X	X
Vital Signs (BP, HR, temp)	X	X	X	X	X	X	X	X	X	X
Zubrod Performance Status	X	X	X	X	X	X	X	X	X	X
Toxicity Assessments 	X	X	X	X	X	X	X	X	X	X
Disease status 	X	X	X	X	X	X	X	X	X	X

 Must be performed within 28 days of initiation of study treatment, unless a different timeframe is specified

 Assessments should be conducted between 4-6 weeks following the last IMRT treatment

 Includes height and body surface area (BSA); height is collected at pre-study visit only

 p16 expression for eligibility must be detected by immunohistochemistry and in situ hybridization (HPV)

 Must be performed within 8 weeks of start of treatment for cancer

 WOCBP must have a negative serum pregnancy test at least 14 days prior to initiation of cancer treatment

 Acute AEs will be collected up to 90 days following the last IMRT; late radiation toxicities will be collected from 3 months up to 3 years following the last IMRT

 Disease status should be assessed at each follow-up, using RECIST criteria

 Assessments should be performed  $\pm$  2 weeks from date

The imaging assessments at 3 months post-IMRT are optional.

 May be completed by mail if patient is not scheduled for or misses a clinic visit

 Follow-up physical exams may include a flexible fiberoptic nasolaryngoscopy

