### **6.3 Toxicity and Safety**

Patients will be evaluated for toxicity and safety weekly during radiation treatments (Section 5.1). Adverse events and other symptoms will be graded according to the National Cancer Institute (NCI) Common Terminology Criteria for Adverse Events (CTCAE) Version 4.0. See Section 8 for more details.

The following additional endpoints for toxicity will also be assessed at the toxicity assessments:

1. Grade of acute radiation dermatitis and late subcutaneous fibrosis (stratified by neck dissection or no neck dissection) in the N0 volumes
2. Late radiation toxicity (events that persist or occur after 90 days of completion of IMRT)
3. Neck dissection complication rate (wound breakdown)
4. Grade of xerostomia
5. Grade of dysphagia
6. Acute and late grade 3 or higher adverse event
7. Rate of PEG dependence at 6 months post-IMRT

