### 7.3 Analyses

Point estimates and confidence interval will be calculated for all dichotomous endpoints (N0 control rate, locoregional control rate, AE specific rates). The Kaplan-Meier product-limit method will be used to estimate PFS and locoregional recurrence-freesurvival. Confidence intervals will be estimated for all efficacy endpoints. Under the assumption of exponential PFS we will estimate the exponential parameter ( $\lambda$ ) and test whether the data support the alternative hypothesis that  $\lambda=0.1335$  versus the null hypothesis that  $\lambda=0.0744$ . Repeated measure models will be used to describe the change over time in QOL as measured by questionnaire. Data from the treatment planning software which produces graphs on mean, max, minimum doses to structures, as well as volumes of particular structures receiving certain doses will be used to compare the dose volume histograms (DVH) of treatment plans for patients receiving 39.6 Gy to the N0 neck to the DVH of matched treatment plans with the standard 50 Gy to the

N0 neck (i.e., to quantify the difference in radiation dose to critical structures in the neck with the decreased dose regimen compared to standard practice).

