#### **7.4 Reporting and Exclusions**

All patients will be evaluable for toxicity and adverse events from the time of protocol intervention (start of treatment).

Evaluation of efficacy – All patients included in the study should be assessed for efficacy endpoints, even if there are major protocol treatment deviations or if they are ineligible. All of the patients who met the eligibility criteria will be included in the main analysis of the efficacy.

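### Late toxicity has no at-risk set or censoring rule: applied as written, the all-treated population and simple proportion would understate late rates for patients lost alive

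*Combined protocol and SAP*

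**What the plan says.** The plan states one toxicity population, in two places. Section 4.3: "Any patient who receives treatment on this protocol will be evaluable for toxicity". Section 7.4: "All patients will be evaluable for toxicity and adverse events from the time of protocol intervention (start of treatment".

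The estimator is in section 7.3: "Point estimates and confidence interval will be calculated for all dichotomous endpoints (N0 control rate, locoregional control rate, AE specific rates". A censoring-based method is named there for two efficacy endpoints only: "The Kaplan-Meier product-limit method will be used to estimate PFS and locoregional" recurrence-free survival.

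Section 6.3 lists late endpoints among the toxicity endpoints: "Late radiation toxicity (events that persist or occur after 90 days of completion of IMRT", late subcutaneous fibrosis, acute and late grade 3 or higher events, xerostomia and dysphagia grade, and "Rate of PEG dependence at 6 months post-IMRT". Footnote 7 to the tables in 5.1 sets the window: "late radiation toxicities will be collected from 3 months up to 3 years following the last IMRT".

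Two further provisions bear on the point. Section 4.7 says "Patients will be followed for three years after completion of the treatment or withdrawal from the study, or until death (whichever occurs first". Section 4.9 allows patients to leave for progression, adverse events, withdrawal and other reasons, and keeps the data gathered up to that point in the final analysis. No section says how a patient with missing or partial late-window assessments is counted.

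**The concern.** Making all treated patients evaluable suits acute toxicity, which arises during or soon after the 7-week course while nearly everyone is being seen. It does not carry over to a window that opens 3 months after treatment and closes at 3 years. A patient lost before day 90 can never have a late event recorded. A patient lost at month 9 has been watched for 6 of the 33 window months (18%). If both stay in the denominator of a simple proportion, they act as non-events for time in which nobody observed them.

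The direction matters. Section 1.1 hypothesises that the lower nodal dose reduces toxicity, and section 1.4 sets out to show better tolerability than historic controls. An understated late rate leans towards that conclusion. If instead the analyst is free to use assessed patients only, the denominator can be chosen after the data are seen.

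**Working it through.** **1. The plan's own figure.** The only precision stated for a dichotomous rate is in 7.2: a two-sided 90% interval of width 0.17 at 10% with 45 patients. The exact (Clopper-Pearson) interval at 4.5 of 45 is 0.038 to 0.206, width 0.168, so it reproduces. It treats all 45 as fully observed. No corresponding figure is given for late toxicity.

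**2. Inputs.** From the documents: n = 45 (7.2), and a window from month 3 to month 36, so 33 months (5.1, footnote 7). Assumed, because the documents do not give them: a true late rate r of 20% or 30% by month 36, and a fraction L lost alive of 5 to 30%. Section 8.1.2 gives only broad frequency bands by event and grade, not tied to the late window. Loss is taken as unrelated to toxicity, and the late-event hazard as constant over the window.

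**3. All loss before the window.** Crude rate = r × (1 − L).

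**4. Loss spread evenly over months 3 to 36, earlier events kept (as 4.9 provides).** Crude rate = r × (1 − L) + L × m. Here m is the average chance that a leaver had an event before leaving: m = 1 − r / (−ln(1 − r)).
- r = 20%: m = 1 − 0.20/0.2231 = 0.104
- r = 30%: m = 1 − 0.30/0.3567 = 0.159

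Example, r = 20% and L = 20%: 0.20 × 0.80 + 0.20 × 0.104 = 0.160 + 0.021 = 0.181.

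| Lost alive | True 20%, lost before day 90 | True 20%, even loss | True 30%, lost before day 90 | True 30%, even loss |
|---|---|---|---|---|
| 5% | 19.0% | 19.5% | 28.5% | 29.3% |
| 10% | 18.0% | 19.0% | 27.0% | 28.6% |
| 20% | 16.0% | 18.1% | 24.0% | 27.2% |
| 30% | 14.0% | 17.1% | 21.0% | 25.8% |

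**5. Other loss patterns.** With a constant loss hazard from the end of IMRT instead, so that some loss falls before day 90, a true 20% reads 18.9% at 10% loss and 17.8% at 20% loss by 3 years. If the whole 20% leave at 1 year, it reads 17.2%.

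**6. Deaths.** With death as a competing event, cumulative incidence = h/(h + d) × (1 − exp(−33(h + d))), with monthly hazards h for toxicity and d for death. For a 20% rate absent death and 10% mortality over the window: 33h = 0.2231, 33d = 0.1054, and 0.679 × (1 − 0.72) = 19.0%. The simple proportion over all patients has the same expectation. Keeping deaths without the event in the denominator is therefore correct for that estimand.

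**7. In patients.** Nine late events are 20.0% of 45 (exact 90% interval 10.9 to 32.3%). If nine patients were lost before the window opened, the same nine events are 25.0% of 36 (13.7 to 39.6%).

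**The case against.** A reader might infer that the plan itself declares leavers free of late toxicity and so builds in a downward bias. The documents do not support that. Sections 4.3 and 7.4 say who is evaluable. The sentence in 4.3 sits among the dose-modification rules and is followed by a reference to scheduled assessments. Section 7.3 names no denominator. Counting leavers as non-events follows only if the stated population and estimator are combined and applied literally. Some endpoints in 6.3 resist a universal denominator: a neck dissection complication rate can only concern patients who had a dissection, and PEG dependence at 6 months reads naturally as a status among those seen then.

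The loss is also limited. Section 4.7 continues follow-up after withdrawal, 4.9 keeps events recorded before leaving, and 7.2 assumes at least 3 years of follow-up, so a late cut-off should not truncate the window. Toxicity is a secondary objective without a planned test, and the criteria in 7.1 for further study concern N0 control, locoregional control and 3-year disease-free survival. At 10% even loss a true 20% reads 19.0%, a gap of 1.0 point, or about 0.4 of a patient in 45. That is far inside the sampling error.

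All of this stands, and it reduces the size of the point. It does not supply the missing rule. Planned follow-up after withdrawal yields nothing for a patient who stops attending or withdraws consent. If the plan can be read either way, the choice still has to be fixed beforehand.

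**Conclusion.** The plan leaves the late-toxicity denominator and the handling of incomplete follow-up undefined. The only population and estimator it does state would understate late rates for patients lost or withdrawn alive. Deaths do not contribute.

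The size rests wholly on assumed loss and an assumed late rate. For a true 20%, the shortfall is about 1 point or less with 5 to 10% even loss, about 2 points with 20% even loss, and 4 points if 20% are lost before day 90. These figures assume that loss is unrelated to toxicity. That the error favours the regimen further assumes that the historic late rates are not diluted in the same way; the documents do not say how those rates would be derived. The point is modest, but it concerns the endpoints on which the tolerability case depends.

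**What to change.** Amend 7.3 and 7.4 as follows.

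- **Acute toxicity:** keep all treated patients as the denominator.
- **Late grade 3+ toxicity and late fibrosis (at a stated grade, keeping the stratification by neck dissection in 6.3):** estimate cumulative incidence among patients under toxicity follow-up at day 90. Count events still present at day 90 as events at the start of the window, because 6.3 includes persisting events. Censor at the last toxicity assessment and treat death without the event as competing.
- **Xerostomia and dysphagia:** report grade by visit among patients alive and assessed, with the number not assessed. These grades can recover, so first-event incidence alone would answer a different question.
- **PEG dependence at 6 months:** report among patients alive and assessed at that visit, with the number not assessed.
- **Loss:** report how many patients left alive, and when. Censoring does not remove bias if patients leave because of toxicity.

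The cost is a few sentences and a routine analysis of assessments already scheduled in 5.1. Reported late rates will be slightly higher and their intervals slightly wider. In the nine-event example, which is an extreme case, the 90% interval widens from 21.4 points (32.3 − 10.9) to 25.9 points (39.6 − 13.7).
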